5. Have a growth disorder of bones or connective tissue, type 1 diabetes mellitus, type 2 diabetes mellitus, or who have a history of carpal tunnel syndrome, trigger finger, myopathy, cancer, endocrine disorder, hypertension or rheumatologic disorder.
6. Systolic blood pressure >140mm Hg or diastolic blood pressure >90mm Hg, or with resting heart rate >110 BPM or <40 BPM at screening.
7. Additionally, because GH is currently listed as a banned substance by the World Anti-Doping Agency (WADA), National Collegiate Athletics Association (NCAA) and most professional sports agencies, we will exclude patients who are current collegiate, professional or elite athletes.

We will recruit up to 48 total patients (24 placebo control, 24 GH), recruited at a rate up to 3 to 6 patients per month. Interim data analysis will be performed, and actual sample sizes may be lower based on safety assessments and the effect of GH on strength.

We will exclude women from this study due to the consequences GH can have on reproductive cycles, and because GH can decrease the efficacy of birth control medications. Additionally, GH could have detrimental effects on a developing fetus. For these reasons, we are excluding women from participation in this study.

Screening Visit and Initial Study Measurements. Patients who consent to surgery and are interested in participating in the study will be seen at a screening visit. The screening visit will typically occur after a normal clinic visit, but may be scheduled at the convenience of the patient. The vital signs of patients will be measured, the history will be recorded, and patients will be asked to report to an M-Labs testing location for fasting blood work within the next 5 days. The labwork includes complete blood count with platelet differential, metabolic panel (glucose, urea nitrogen, creatinine, sodium, potassium, chloride, CO₂, calcium, total protein, albumin, total bilirubin, AST, ALT and alkaline phosphatase), lipid panel (total cholesterol, triglycerides, HDL cholesterol, LDL cholesterol), hemoglobin A_{1c}, high sensitivity CRP, creatine kinase, and IGF-1 (as described below). Patients who have normal values based upon M-Labs guidelines will be permitted to enroll in the study. Patients with minor deviations (typically less than 10%) from normal values may be allowed to participate based on consultation with [name] and [name]. Patients who do not pass screening will be provided with \$25 compensation.

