Blood Draw. Approximately 6-8mL of blood will be drawn from an antecubital vein and collected into either a K₂-EDTA tube for plasma preparation or a clot activator tube for serum preparation. A portion of the plasma or serum will be used for clinical labs performed by UMHS M-Labs and a portion will be stored at -80°C for measurement of different proteins in [name] lab. The tests performed by M-Labs include a complete blood count with platelet differential, metabolic panel (glucose, urea nitrogen, creatinine, sodium, potassium, chloride, CO₂, calcium, total protein, albumin, total bilirubin, AST, ALT and alkaline phosphatase), lipid panel (total cholesterol, triglycerides, HDL cholesterol, LDL cholesterol), hemoglobin A_{1c}, high sensitivity CRP, creatine kinase, and IGF-1. For measurements performed in [name] lab, the levels of myostatin (as a marker of muscle atrophy), MMP-3 (as a marker of cartilage catabolism), and hyaluronic acid (as a marker of cartilage catabolism) will be measured in duplicate using ELISAs as described (Mendias 2013).

Vital Signs. Patients' heart rate, temperature, blood pressure and respiratory rate will be recorded at each visit.

Wallet Card. Patients will be provided with a laminated card to carry in their wallet or purse in case of emergencies. The card will state that the patient is currently enrolled in a clinical trial evaluating GH, that they are taking either GH or placebo and the contact information for [name], [name], [name] and the study research coordinator.

Administration of GH or Placebo. The UMHS Pharmacy IDS service will be used to assist with storing, preparing and dispensing drug. We will use Humatrope (somatropin of rDNA origin, Eli Lilly) as the test drug, and sterile bacteriostatic saline with no active hormone will serve as the control. We will use sterile insulin syringes to deliver drug or placebo subcutaneously. Patients will be provided with the manufacturer's instructions for the use of Humatrope, all supplies (needles, alcohol swabs, cartridges containing GH or placebo, disposal container) and will also receive personalized instruction on how to

prepare and deliver GH using a mock system by study personnel. Patients will be instructed to rotate injection sites to minimize discomfort.

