
Adjustment of Dose for Musculoskeletal or Other Minor Side Effects. For subjects who develop minor musculoskeletal side effects, such as carpal tunnel syndrome or trigger finger, or other minor side effects such as mild hypoglycemia or hyperglycemia (glucose lower than 65 mg/dL or greater than 100 mg/dL) mild headaches, fluid retention, peripheral swelling, and joint pain in the unoperated leg or other area of the body (these symptoms are likely to be present in the operated limb as a result of surgery) the dose of GH or placebo will be reduced to 0.25mg per BSA BID. For patients

with carpal tunnel or trigger finger, they will also receive treatment consisting of ice (15-20 minutes twice daily) and range of motion exercises, which are the standard care for the onset of carpal tunnel or trigger finger. If the symptoms/abnormal values resolve in 7-10 days, the dose will then be titrated as tolerated at increments of 0.05mg per BSA BID every 7 days until reaching a dose at which symptoms do not appear/abnormal values return to normal, or upon reaching the normal study dose of 0.5mg per BSA BID. If symptoms/abnormal values persist at the dose of 0.25 mg per BSA BID greater than 7-10 days, the dose will be decreased to 0.1 mg per BSA BID and titrated up at increments of 0.05mg per BSA BID every 7 days until reaching a dose at which symptoms do not appear/abnormal values return to normal levels. If symptoms/abnormal values do not resolve after 7-10 days at a dose of 0.1mg per BSA BID, the subjects will be discontinued from the study.

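### The dose cut for glucose above 100 mg/dL does not require a fasting sample, and a cut made at Postop 1 or 2 cannot be fully reversed before dosing ends

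*Combined protocol and SAP*

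**What the plan says.** **The trigger.** The section on adjusting the dose for musculoskeletal or other minor side effects lists "mild hypoglycemia or hyperglycemia (glucose lower than 65 mg/dL or greater than 100 mg/dL" among the events that lead to a cut. For any of them, "the dose of GH or placebo will be reduced to 0.25mg per BSA BID". It mentions neither a fasting state nor a repeat sample.

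**The way back.** "If the symptoms/abnormal values resolve in 7-10 days, the dose will then be titrated as tolerated", in steps of 0.05 mg/m² twice daily every 7 days. Titration stops at a dose without symptoms or abnormal values, or "upon reaching the normal study dose of 0.5mg per BSA BID". If the abnormality persists at 0.25 mg, "the dose will be decreased to 0.1 mg per BSA BID and titrated up" in the same steps. If it still does not resolve, the subject is discontinued.

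**Sample condition.** At screening, "patients will be asked to report to an M-Labs testing location for fasting blood work within the next 5 days". The Blood Draw section opens with "Approximately 6-8mL of blood will be drawn from an antecubital vein" and lists the same panel, glucose included, without the word fasting. Table 1 lists a plain blood draw at Postop 1, 2 and 3 (about 1, 2 and 5 weeks after surgery).

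**Dosing period.** Under Administration of GH or Placebo, treatment runs from one week before surgery through five weeks after it, with no dose on the day of surgery.

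**The concern.** The glucose limit drives a mandatory action, yet the plan does not say what kind of sample it applies to. The same panel is specified as fasting at screening, so the protocol already treats sample condition as relevant. It leaves the condition open at the visits where the number sets the dose.

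Two things are at stake. First, the leading objective under Outcome Measures is whether GH is safely tolerated, and Risks of Participation lists glucose intolerance as a GH risk. Values raised by a meal would be counted as side effects and dose reductions in both arms, which blurs that comparison. Second, in the GH arm an unneeded cut removes active drug, and the titration schedule may be too slow to restore it within a six-week course.

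**Working it through.** **Inputs.** Full dose 0.5, cut dose 0.25 and step 0.05 (mg/m² per injection, twice daily); wait of 7–10 days; one step every 7 days (dose-adjustment section). Dosing for 1 week before and 5 weeks after surgery (Administration of GH or Placebo). Visits at about weeks 1, 2 and 5 (Table 1).

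**Dosing days.** 7 + 35 = 42, which reproduces the stated six weeks. Planned total per injection slot: 42 × 0.5 = 21 mg/m². Counting 41 days instead changes the shares below by about 1 point or less.

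**Dosing days left.** After Postop 1: 35 − 7 = 28. After Postop 2: 35 − 14 = 21. Postop 3 falls at the end of dosing, so a cut there changes almost nothing.

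**Time back to full dose.** (0.50 − 0.25)/0.05 = 5 steps. The text does not say whether the first step is taken on resolution (reading A) or 7 days later (reading B).
- A: wait + 4 × 7 = 35 days (7-day wait) or 38 days (10-day wait)
- B: wait + 5 × 7 = 42 or 45 days

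All four exceed 28 and 21. Under A, full dose is regained for at least one day only if the cut comes after no more than 42 − 35 − 1 = 6 dosing days (7-day wait) or 42 − 38 − 1 = 3 (10-day wait). Under B it is never regained. Table 1 has no on-treatment draw that early: Preop 2 has no blood draw, and the Preop 1 draw precedes dosing.

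**Share of planned dose delivered if the value resolves.**

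| Cut at | Reading, wait | Dose after the cut (days × mg/m²) | Share | Last dose |
|---|---|---|---|---|
| Postop 1 (14 × 0.5 = 7.0 before) | A, 7 d | 7×0.25 + 7×0.30 + 7×0.35 + 7×0.40 = 9.10 | 16.10/21 = 76.7% | 0.40 |
| | A, 10 d | 10×0.25 + 7×0.30 + 7×0.35 + 4×0.40 = 8.65 | 15.65/21 = 74.5% | 0.40 |
| | B, 7 d | 14×0.25 + 7×0.30 + 7×0.35 = 8.05 | 15.05/21 = 71.7% | 0.35 |
| | B, 10 d | 17×0.25 + 7×0.30 + 4×0.35 = 7.75 | 14.75/21 = 70.2% | 0.35 |
| Postop 2 (21 × 0.5 = 10.5 before) | A, 7 d | 7×0.25 + 7×0.30 + 7×0.35 = 6.30 | 16.80/21 = 80.0% | 0.35 |
| | A, 10 d | 10×0.25 + 7×0.30 + 4×0.35 = 6.00 | 16.50/21 = 78.6% | 0.35 |
| | B, 7 d | 14×0.25 + 7×0.30 = 5.60 | 16.10/21 = 76.7% | 0.30 |
| | B, 10 d | 17×0.25 + 4×0.30 = 5.45 | 15.95/21 = 76.0% | 0.30 |

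**Effect on the arm mean.** With 24 patients per arm, each GH patient cut at Postop 1 whose value resolves lowers the arm's mean delivered dose by (100 − 76.7)/24 = 0.97 to (100 − 70.2)/24 = 1.24 percentage points.

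**The recheck.** Whether a value resolves or persists is judged with the same undefined sample. After a Postop 1 cut, the Postop 2 draw falls about 7 days later and can serve. After a Postop 2 cut, no scheduled draw falls 7–10 days later; the next is at about week 5.

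**The case against.** The strongest reply is that silence is not a non-fasting draw. The screening section refers forward to the laboratory description, so the Blood Draw section seems to cover the fasting screening sample too, without using the word. On-treatment draws may well be fasting in practice. This stands: a reader might infer that the protocol contradicts itself or specifies non-fasting samples, and the documents support neither.

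Second, the rule is for subjects who develop side effects. Lab reports go to a named recipient as they occur, and the safety committee includes an endocrinologist (Data and Safety Monitoring Plan). Someone could ask whether the patient had eaten. But nothing requires it, and the rule as written calls for the cut.

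Third, a reader might infer that the titration schedule fails because it cannot restore 0.5 mg. It does not fail on its own terms: titration is as tolerated, and a lower tolerated dose is an accepted endpoint. The schedule also covers every other listed side effect. It matters here only because it does not undo an unneeded glucose cut.

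Fourth, the rule is blinded and identical in both arms, raw glucose is recorded, and hemoglobin A1c is measured as well. So the blurring concerns the count of side effects and dose cuts, not all the glycemic safety data. A low limit with a quick cut is a defensible choice in a pilot.

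**Conclusion.** The gap is real and minor. As written, a meal-affected glucose above 100 mg/dL can halve the dose and be handled as a side effect. No reading of the titration text restores 0.5 mg/m² after a cut at Postop 1 or Postop 2. If the value resolves, delivered dose is about 70–77% or 76–80% of plan. The width of these ranges reflects the 7–10 day wait and the unstated timing of the first step; they also assume 42 dosing days and visits on their nominal days.

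A reader might go further and infer that many patients would be cut, or that the 26-week strength comparison would be biased. The documents give no trigger frequency and no dose-response for strength, so neither can be estimated or claimed.

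**What to change.** - **Blood Draw:** state that glucose at the on-treatment visits (Postop 1 to 3) is drawn fasting, as at screening.
- **Dose-adjustment section:** define the high-glucose trigger as a fasting value above 100 mg/dL, and judge resolution or persistence on a fasting value too. If the patient has eaten, a high value leads to a prompt fasting redraw before the cut.
- **Leave unchanged:** the low-glucose rule, the severe-hyperglycemia rule in the Data and Safety Monitoring Plan, and the titration steps.

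A routine repeat of a value already taken fasting is optional. It trades safety speed for certainty and is not part of the required change.

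**Cost.** Two or three sentences, and fasting before three existing draws. At Postop 3 fasting serves only the safety comparison, since dosing is ending. A redraw briefly delays a true cut: each day at 0.5 instead of 0.25 mg/m² adds 2 × 0.25 = 0.5 mg/m², so an assumed delay of 2–4 days adds 1–2 mg/m² in total. The check 7–10 days after a Postop 2 cut needs an unscheduled draw, but the existing rule already implies one.

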Randomization and Assignment of Groups. Patients will be assigned to placebo or GH treatment groups using a block randomized assignment schedule that maintains equal group sizes. All included patients will be assigned unique identification numbers by [name], clinical research coordinator in [name] lab, with no involvement in this study design or interpretation of any resultant data. [name] will then assign identification numbers in a consecutive fashion to either group "maize" (randomly designated by [name] as either the placebo or treatment group) or group "blue" (the group not selected to be represented as group A). [name] will keep all patient names and assigned identifier lists private in a sealed envelope in a locked cabinet as well as on two separate passcode protected hard drives. He will make the unblinded group identities available to [name], relevant members of the UMHS Pharmacy IDS and safety board members if necessary. Therefore, the patients, investigators, attending physicians, those measuring outcome will be unaware of the allocation of the patients and thus will be blinded.

Risks of Participation. There are some potential risks of GH that will be closely monitored. The risks include: glucose intolerance or reduced insulin sensitivity, fluid retention and peripheral swelling, joint pain, headache, numbness or fatigue, tissue atrophy, pancreatitis, intracranial hypertension, injection site lipoatrophy, and local or systemic allergic reactions. The injection of GH might infrequently cause some slight discomfort and there is a rare risk of infection from injections. There are minimal risks associated with the blood draws -- the needle stick may infrequently hurt and cause bruising, and a rare risk of local infection. There are no known harmful effects from the strong magnetic field used for MRI, although any loose metal object has the risk of causing damage or injury if it gets pulled toward the strong magnet. Strength measurements might infrequently cause some soreness that would last less than a day.

Benefits of Participation. If our hypothesis is supported, patients that receive GH will have improved recovery after ACL-R.

Payment to Subjects. Patients will also receive \$1000 for participating in the study. Patients who drop out prior to completion will receive a pro-rated amount (\$125 per visit).

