Data and Safety Monitoring Plan. We will have a committee to oversee the safety and adverse events that may come up in this study. The committee will consist of [name] (endocrinologist), [name] (sports medicine orthopaedic surgeon), and [name] (primary care/sports medicine). All lab reports will be sent to [name] as they occur, and the full committee will review outcomes and patient (surveys, strength measurements, M-Labs blood work reports, injuries, etc.) every 3 months (or as needed) and review. If an excessive number of adverse events or infrequent but serious events happen, the committee will have the ability to halt the study or unenroll patients from the study. The committee may also stop the trial if there are any concerns that GH is causing harm. These potentially serious events that would cause the patient to unenroll from the study include any vital signs rising to levels above those described in the exclusion criteria, or signs of intracranial hypertension, severe fluid retention, severe hyperglycemia. These are potentially serious side effects described from previous clinical trials of GH, and although we cannot predict all potentially serious side effects, we will rely on the clinical expertise of the safety monitoring team to assess any other potentially serious but unexpected risks. In these situations the random code will be broken for that patient and any required care for them will then be initiated. Unblinding for all study team members will occur after the last patient has been discharged from care.

At the conclusion of the study, original data will be archived in the UM Department of Orthopaedic Surgery following FDA guidelines.

Adverse Event Reporting Timetable. We will follow the standard IRB adverse events reporting timeline. Adverse events that are expected and non-serious will be reported to the safety committee at their regular meetings, and to the IRB as part of the scheduled continuation application. Serious adverse events will be reported to the safety committee immediately, and to the IRB within 7 days, and to the FDA as per the regulations.

Regulatory Affairs Coordinator. [name], clinical research manager in the Department of Orthopaedic Surgery, will coordinate safety committee meetings and ensure the study maintains regulatory compliance with federal and state laws, and UM policies.

References

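### Safety rules remove patients from the study, not just from the drug, so week-26 strength is lost for patients selected partly by GH side effects

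*Combined protocol and SAP*

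**What the plan says.** Two rules end study participation.

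- **Data and Safety Monitoring Plan.** Events that would "cause the patient to unenroll from the study include any vital signs rising to levels above those described in the exclusion criteria" are listed together with signs of intracranial hypertension, severe fluid retention and severe hyperglycemia. The text continues: "These are potentially serious side effects described from previous clinical trials of GH". On what follows removal it says: "In these situations the random code will be broken for that patient and any required care for them will then be initiated".
- **Adjustment of Dose for Musculoskeletal or Other Minor Side Effects.** Minor effects, among them "mild hypoglycemia or hyperglycemia (glucose lower than 65 mg/dL or greater than 100 mg/dL"), lead to a reduction to 0.25 mg per BSA BID. If they "persist at the dose of 0.25 mg per BSA BID greater than 7-10 days", the dose falls to 0.1 mg. If they "do not resolve after 7-10 days at a dose of 0.1mg per BSA BID, the subjects will be discontinued from the study".

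The vital-sign limits are those of exclusion criterion 6: systolic pressure above 140 mm Hg, diastolic above 90, heart rate above 110. Vital signs are taken at every visit. Under Risks of Participation the protocol says of GH: "The risks include: glucose intolerance or reduced insulin sensitivity, fluid retention and peripheral swelling, joint pain, headache".

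Dosing runs from one week before surgery to five weeks after it. The primary outcome is isokinetic knee extension strength at 26 weeks. Table 1 has no strength test between the pre-operative one and about week 5. The sample size section adds 7 patients per group for attrition and names a mixed-effects model. It gives no analysis set and no rule for missing data.

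**The concern.** Leaving the study is decided after randomisation, for reasons the protocol largely attributes to the active drug. If more GH than placebo patients are removed, the week-26 comparison is no longer between the groups as randomised. The seven extra patients per group restore numbers but do not stand in for the particular patients lost.

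The first objective is also affected. The study asks whether GH is safely tolerated, and the patients with the most informative events leave the scheduled labs, vital signs and surveys. Their triggering event is still reported and clinical care continues; what is lost is systematic follow-up afterwards.

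One point needs clarifying. The vital-sign rule has no stated time limit and does not say whether a reading must be confirmed. Read literally, it could remove patients at week 12 or 18, when there is no drug left to stop. The authors may have meant the dosing period only. Losses after dosing would be avoidable loss rather than bias.

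**Working it through.** **Planned effect.** The plan states 17 per group for a 30% difference at 80% power and alpha 0.05, but gives no SD, so 17 cannot be reproduced from its own inputs. Solving the two-sided t-test for 17 per group and 80% power gives a standardised effect d = 0.991. The recruitment step does reproduce: 17 + 7 = 24 per group, 48 in all. The attrition reserve is 7/24 = 29%.

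**Timing of the dose-adjustment route.** The minimum is 7 days at 0.25 mg plus 7 days at 0.1 mg, or 14 days from the first reduction. No upper limit is fixed, because the first window is open-ended. With surgery on dosing day 7, the week-5 test is at about day 7 + 35 = 42. A first reduction on day 21 allows removal from day 21 + 14 = 35, before that test. Reductions in the first three weeks of dosing can therefore end in a patient with baseline strength only.

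**Bias.** For patients with only baseline strength, bias = f × δ. Here f is the excess share of the GH arm removed, and δ is the difference in week-26 strength, in SD, between removed and retained patients with the same baseline. Both are assumed.

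| Excess GH removals of 24 | f | δ = 0.5 SD | δ = 1 SD | Share of 0.991 |
|---|---|---|---|---|
| 1 | 0.042 | 0.021 | 0.042 | 2–4% |
| 2 | 0.083 | 0.042 | 0.083 | 4–8% |
| 4 | 0.167 | 0.083 | 0.167 | 8–17% |

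A baseline-adjusted simulation reproduced f × δ to within 0.002. The direction is unknown.

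**Loss under a literal vital-sign rule.** Five post-operative visits precede week 26 (weeks 1, 2, 5, 12, 18). With an assumed chance p per visit of exceeding a limit, the share removed is 1 − (1 − p)^5 if visits are independent. A beta-binomial model with within-patient correlation 0.3 gives less. Power is the t-test at d = 0.991 with 24 × (1 − loss) per arm.

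| p per visit | Visits | Removed by week 18 | Left per arm | Power | Removed at week 1 or 2 |
|---|---|---|---|---|---|
| 2% | independent | 9.6% | 21.7 | 89% | 4.0% |
| 5% | independent | 22.6% | 18.6 | 84% | 9.8% |
| 10% | independent | 41.0% | 14.2 | 72% | 19.0% |
| 2% | correlation 0.3 | 5.9% | 22.6 | 90% | 3.4% |
| 5% | correlation 0.3 | 14.4% | 20.6 | 87% | 8.3% |
| 10% | correlation 0.3 | 27.1% | 17.5 | 81% | 16.3% |

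This rule alone would use up the 29% reserve at p = 6.7% (independent) or 10.9% (correlation 0.3), and the reserve must also cover other losses. Removals at weeks 12 and 18, if the rule applies then, come to 1.8, 4.0 or 6.6 of 48 (independent), or 0.7, 1.7 or 3.0 (correlation 0.3).

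**The case against.** The case against has several fair parts.

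- **Silence is not prohibition.** The plan does not forbid a week-26 test after removal. True, but it does not provide one either, and both rules speak of leaving the study.
- **Removals may be few.** Participants are men aged 18 to 35 screened for blood pressure and heart rate, and two dose reductions come before removal for minor effects. The committee can use judgement. This stands as a limit on size. The vital-sign rule, however, has no intermediate step, and its wording is close to automatic.
- **The arm difference is weakest for vital signs.** The GH risk list names neither blood pressure nor heart rate, and pain after surgery could raise readings in both arms. This stands in part; the only link is the general sentence calling the listed events GH side effects. The link is firmer for glucose, fluid retention and joint pain. The joint-pain trigger does exclude the operated limb.
- **The dose-adjustment route before week 5 needs checks between visits.** Scheduled visits during post-operative dosing fall at about days 14, 21 and 42. Correct, but the section's own 7-10 day windows imply such checks.
- **The bias is small.** The standard error is about √(2/24) = 0.29 SD at 24 per arm, so even 0.083 SD is under 0.3 standard errors, in a pilot. This stands and keeps the point from being critical. It is no reason to leave an avoidable selective loss in place.

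**Conclusion.** The concern holds. Following the two rules as written loses the primary outcome for patients removed for events the protocol largely attributes to GH, and neither the attrition reserve nor the mixed model fully repairs that. The wording is certain; the size is not. Under assumed excess removals of 1 to 4 of 24 before week 5 and an assumed difference of 0.5 to 1 SD, the shift is 0.02 to 0.17 SD, or 2% to 17% of the implied effect, in either direction. Power is the lesser concern: it falls below 80% only in the harshest case shown (10% per visit, independent visits, every reading acted on). This should be fixed because the remedy is cheap, not because the likely bias is large.

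**What to change.** In the dose-adjustment section and the Data and Safety Monitoring Plan, replace removal from the study with stopping study drug. Then:

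1. State that the vital-sign stopping rule applies during dosing; a later high reading leads to clinical care. The safety committee should agree this, since it settles the scope of a safety rule.
2. Keep these patients in the scheduled visits to week 26 unless they withdraw consent, omitting any test judged unsafe.
3. Keep code-breaking as a safety measure. The randomisation section promises that "those measuring outcome will be unaware of the allocation of the patients and thus will be blinded". Where a code is broken, keep the strength assessor blinded if possible, record the unblinding, and show the primary result with and without those patients. The result without them is a sensitivity analysis only, because it repeats the selective exclusion.
4. State in the statistical section that all randomised patients are analysed in their assigned arm.

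Thresholds and dose steps do not change.

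**Cost.** Protocol wording and a line in the consent form. The visits are already scheduled: at most 6 × $125 = $750 per patient, within the $1000 planned. There are two downsides. The first is dilution. If 2 or 4 of 24 GH patients stop early and gain nothing (worst case), the effect is 0.991 × 22/24 = 0.91 or 0.991 × 20/24 = 0.83 SD, and power with 24 per arm falls from 92% to 87% or 80%. The second is that some effort-dependent week-26 strength tests would come from patients whose code was broken.
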